**Additional questions for post evaluation**

12. What are the 7-steps of hand washing? (MC Questions)

	A	B	C	Answers
Step 1	Finger tips	Palms	Between fingers	Palms
Step 2	Back of hands	Back of fingers	Palms	Back of hands
Step 3	Thumbs	Finger tips	Between fingers	Between fingers
Step 4	Palms	Between fingers	Back of hands	Back of fingers
Step 5	Finger tips	Thumbs	Back of fingers	Thumbs
Step 6	Back of fingers	Finger tips	Wrists	Finger tips
Step 7	Wrists	Thumbs	Back of hands	Wrists

13. What is the sequence for hand hygiene?

Steps		Drag Answer Here:
Finger tips	Step 1	
Back of hands	Step 2	
Thumbs	Step 3	
Palms	Step 4	

Protocol

Date 1 May 2023

Finger tips	Step 5	
Back of fingers	Step 6	
Wrists	Step 7

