#### Group B (Video training)

Participants will watch a training video about the 7 steps of hand washing after the first HW attempt, but they will not be informed about their hand scanner results.

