#### Group D (Control group without intervention)

Participants will not be informed about the hand scanner results in the first HW attempt and no training videos will be provided.

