### *Post-intervention assessment*

The participants will take the second HW attempt by putting fluorescent powder on both of their hands again and then perform hand wash with videos recorded. Digital images of hands will again be taken under UV light before and after hand wash. After washing hands, participants will scan fluorescent residual remained on their hands again in a hand scanner.

Participants will also be asked to fill in a questionnaire on knowledge and practice of hand hygiene as part of post-intervention assessment.

For the training purpose, after the completion of post-intervention measurements, the participants of the control group (Group D) will watch the training video and repeated hand washing and scanning for the third time if they agree. But the results of their third HW attempt will not be included into data analysis in this

Protocol  
Date 1 May 2023

study.

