**Part II: Hand hygiene**

5. Have you ever received formal training in hand hygiene?

Yes      No

If your answer is yes; when did you receive the training (give the latest year)?

Answer: \_\_\_\_\_ (yyyy)

6. How many steps are required for healthcare workers to perform hand hygiene (please give a number) ?

Answer: \_\_\_\_\_

7. How many types of hand hygiene are there (please give a number)?

Answer: \_\_\_\_\_

8. How long is the minimal duration of hand washing?

Answer: \_\_\_\_\_ seconds

- 9: Which of the following sequence is correct for hand hygiene? (MC Question)

A	Ans: B	C
Finger webs	Finger webs	Thumbs
Finger tips	Back of fingers	Finger tips
Back of fingers	Thumbs	Finger webs

Protocol

Date 1 May 2023

Thumbs	Finger tips	Back of fingers
--------	-------------	-----------------

10. Which of the following is one of hand hygiene steps EXCEPT?

- Rub palms
- Rub fingernails
- Rub wrists
- Fingers interlocked

11. Do you agree or disagree with the following statement:

Hand hygiene is part of infection prevention and control in healthcare settings.

- Strongly agree
- Agree
- Neither agree nor disagree
- Disagree
- Strongly disagree

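### Items 12 and 13, added to the post-intervention questionnaire, can reveal the answer to item 6 to students who saw no video, unless item 6 is submitted before they are seen

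*Protocol*

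**What the plan says.** The Appendix, Part II, item 6, asks for an open number: "How many steps are required for healthcare workers to perform hand hygiene". Under the heading "Additional questions for post evaluation" the protocol then adds two items. The stem of item 12 is "What are the 7-steps of hand washing? (MC Questions", and its rows run from Step 1 to Step 7. The stem of item 13 is "What is the sequence for hand hygiene"; it gives no number, but the answer area has seven numbered slots.

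The post-intervention form is not limited to particular groups. The section on post-intervention assessment says: "Participants will also be asked to fill in a questionnaire on knowledge and practice of hand hygiene as part of post-intervention assessment".

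The groups differ in what they have seen by then. For Group B the protocol says "Participants will watch a training video about the 7 steps of hand washing after the first HW attempt", and Group C sees the same material. Group A gets scanner feedback without a video. For Group D, "no training videos will be provided"; that group is offered the video only once its post-intervention measurements are complete.

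Objective 1 in the Background names knowledge of hand hygiene as something the trial tests, and objective 2 asks for the effect of each component.

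**The concern.** Because the two items are described as additional, the natural reading is that they join items 1 to 11. The post form then asks for the number of steps and also displays it, while the pre form displays it nowhere.

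The cue does not fall evenly on the groups. Students in Groups B and C have just been taught seven steps, so few of them need it. Groups A and D hold more students who do not know the number and could take it from the form. Any use of the cue would therefore raise item 6 mainly where there was no video. Two comparisons are at stake on this item: the video contrast (B and C against A and D), which would move toward zero, and the pre-to-post gain in the non-video groups, which would be inflated. Analysis cannot later separate a copied answer from a known one.

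**Working it through.** The protocol states no expected rate, effect size or power for the questionnaire, so there is no figure to reproduce. The check covers direction first, then size under stated assumptions.

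**Inputs**
- The presumed correct answer to item 6 is seven, inferred from the video content. No key is printed for this item.
- pV and pN are the shares who truly know the number with and without the video (assumed).
- c is the share of those who do not know it who take it from items 12 or 13 (assumed equal in all groups).

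**Formulas**
- Observed share correct = p + (1 - p)c.
- Observed video difference = [pV + (1 - pV)c] - [pN + (1 - pN)c] = (pV - pN)(1 - c).
- False pre-to-post gain in a non-video group whose true knowledge does not change = (1 - pN)c.

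When pV exceeds pN, the difference moves toward zero for every c above 0 and is unchanged at c = 0. The direction does not depend on the rates chosen.

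**Size with pV = 90% and pN = 50%**

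| c | Video groups | Non-video groups | Difference (points) | False gain, Group D (points) |
|---|---|---|---|---|
| 0 | 90% | 50% | 40 | 0 |
| 0.1 | 91% | 55% | 36 | 5 |
| 0.5 | 95% | 75% | 20 | 25 |
| 1 | 100% | 100% | 0 | 50 |

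**Size with pV = 90% and pN = 70%**

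The difference is 20, 18, 10 and 0 points for the same values of c. The false gain is (100 - 70) x c = 0, 3, 15 and 30 points.

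**Equal c is not essential.** With separate shares cV and cN, the difference changes by (1 - pV)cV - (1 - pN)cN. At 90% and 50% this is 0.1cV - 0.5cN, which is negative unless cV is at least five times cN.

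**Reach within the knowledge questions.** Items 6 to 10 are the five factual items in Part II. If they were averaged with equal weight (an assumption, since no scoring rule is given), a 20-point loss on item 6 would be 20/5 = 4 points on the average.

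**The case against.** The strongest reply is about order. Item 6 comes six places before item 12, so a student who works straight through has already answered it. The cue acts only if students read ahead or go back and change an answer. The protocol neither allows nor prevents this, and on a form that moves forward only the bias is exactly zero. The Appendix is also not the layout as fielded: it prints the key for items 9 and 12, so it is an annotated item list, and nobody can tell from it which items share a page. The dragging instruction in item 13 points to an on-screen form, where separating pages is easy.

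Most of this stands, and it makes the point conditional. It does not remove it. On-screen delivery does not by itself block scrolling or going back, so the protection would be assumed. The wording and order of the items are fixed in this document, and a statistical analysis plan could not undo a cue received while the form was being filled in.

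A reader might infer more than the document supports:
- **That item 6 is certainly biased.** This needs students to use the cue, which is not shown.
- **That both items state the number.** Only the stem of item 12 does; item 13 shows seven slots.
- **That Groups A and D can learn the number only from these items.** Item 5 asks about earlier formal training, so some may arrive knowing it.
- **That item 6 is explicitly repeated and scored at both times.** Repetition is a strong inference from the heading over the added items, and no scoring rule is printed.

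**Conclusion.** The point holds in conditional form. If the post form consists of items 1 to 11 plus items 12 and 13, and item 6 can still be answered or changed once those are visible, the form can supply the answer to students who saw no video. The video contrast on item 6 would then be biased toward zero by the factor (1 - c), and the pre-to-post gain on that item in Groups A and D would be inflated by (1 - pN)c.

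The direction follows from the algebra; the size is not known. Under the 90% and 50% assumption the difference ranges from the full 40 points down to 0, and the false gain in Group D from 0 to 50 points, across the whole range of c. A reader might take the upper part of that range as an estimate. The protocol offers no rate for knowledge or for copying, so nothing supports choosing one end.

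Only this one knowledge item is shown to be affected. The hand scanner residual, which the protocol uses as its objective measure of washing, is not. This is a minor improvement to the instrument, worth making because it is nearly free and must be made before data are collected.

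**What to change.** Either of two changes is enough:

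- Present items 12 and 13 on a separate page or sheet, only after items 5 to 11 have been submitted, with no return to earlier answers. State this in the section on post-intervention assessment or in the Appendix.
- Otherwise, take the number out of the stem of item 12 and replace the seven fixed step rows and slots in items 12 and 13 with a format that does not show how many steps there are.

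The first is a form setting, or a second sheet if paper is used, plus one sentence in the protocol. The second means rewording two items. Neither adds visits, participants or measurements.

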**NCT05872581**

**Date: 1 May 2023**

## Background

The ongoing COVID-19 pandemic has posed serious threats to public health worldwide. Although children have mild symptoms, they have been found to more likely transmit the virus within the household than the other age groups. The importance of hand hygiene cannot be underestimated in both healthcare and community settings (Allegranzi et al., 2011; Mathur, 2011). The promotion of hand hygiene is the best practices in preventing health care-associated infection (WHO, 2009). It has been estimated that hand hygiene could reduce over 500 000 attributable deaths per year. It was found that the annual economic impact of health care-associated infection in the US was approximately US\$6.5 billion in 2004 (WHO, 2009) and every US\$1 spent on hand hygiene promotion could result in a US\$23.7 benefit (Chen et al., 2011). Education plays a key role in setting a good practice base in hand hygiene.

The traditional training methods for nursing students include in-class lecture and practical, but students seldom receive individualized instructions and feedbacks due to limited manpower and facilities. Hence, there is an urgent need of designing an automated and individualized education program. This study aims to design and test a multicomponent education program of hand hygiene in nursing students. Specifically, this program has two components: 1) training videos according to the WHO guidelines on hand hygiene in health care (<https://polyu.ap.panopto.com/Panopto/Pages/Viewer.aspx?id=f3973cee-bcfb-48fd-a306-b6893dacaabd>); 2) a hand scanner used for students to immediately visualize the missing spots of hand hygiene.

This study has the following specific objectives:

- 1) conduct a randomized controlled trial (RCT) to test the effectiveness of this program on knowledge and practice of hand hygiene in nursing students;
- 2) evaluate the effects of each component and collect feedbacks from participants.

If demonstrated effective, this program can be integrated into the curriculum of nursing students as an e-learning approach. In future, this system can also be used at point-of-care for real-time monitoring and audit of healthcare workers in other healthcare settings.

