#### Group C (Hand scanner + Video training)

Participants will be informed about their hand scanner results during the first HW attempt. They will also watch a training video about the 7 steps of hand washing.

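### Post-test Q12 does not offer its own keyed answer at step 4, and the Q13 labels repeat Finger tips and omit Between fingers, so neither 7-step item can be answered in full

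*Protocol*

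**What the plan says.** The first objective (protocol, Background) is to "test the effectiveness of this program on knowledge and practice of hand hygiene in nursing students". Knowledge is measured by the questionnaire in the Appendix, which is completed before and after the intervention. Two further items appear only afterwards, under "Additional questions for post evaluation".

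- **Q12** asks for the seven steps of hand washing. Each step has options A, B and C, and a fourth column gives the answer. The step 4 row is "Step 4 Palms Between fingers Back of hands Back of fingers".
- **Q13** asks "What is the sequence for hand hygiene" and gives seven labels to drag into steps 1 to 7. No key is printed for it.

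The content of these items is what the video teaches. For Group B: "Participants will watch a training video about the 7 steps of hand washing after the first HW attempt". For Group C: "They will also watch a training video about the 7 steps of hand washing". Groups A and D do not see the video before the post-test.

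**The concern.** The two items contradict the answer key printed beside them. At step 4 of Q12 the right answer cannot be chosen. In Q13 the right sequence cannot be built from the labels supplied.

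This matters because Q12 and Q13 are the only questions that ask for the complete 7-step sequence. Q6 asks only for the number of steps, Q9 covers the order of four sites, and Q10 asks which option is not a step. Q12 and Q13 are thus the items closest to the video content, where a difference between the video arms (B, C) and the others (A, D) would be expected to show most clearly. If those who learned the sequence cannot record it, that difference is compressed. An analysis plan can decide how to score the items, but it cannot recover a response that was never on offer.

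**Working it through.** **Inputs.** All come from the protocol Appendix: the Q12 options and answers, the Q13 labels, and the Q9 key. I assume that participants see columns A to C of Q12 but not the answers.

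**Q12, row by row**

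| Step | A | B | C | Key | Offered? |
|---|---|---|---|---|---|
| 1 | Finger tips | Palms | Between fingers | Palms | yes (B) |
| 2 | Back of hands | Back of fingers | Palms | Back of hands | yes (A) |
| 3 | Thumbs | Finger tips | Between fingers | Between fingers | yes (C) |
| 4 | Palms | Between fingers | Back of hands | Back of fingers | **no** |
| 5 | Finger tips | Thumbs | Back of fingers | Thumbs | yes (B) |
| 6 | Back of fingers | Finger tips | Wrists | Finger tips | yes (B) |
| 7 | Wrists | Thumbs | Back of hands | Wrists | yes (A) |

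The highest possible score is 6 of 7. Reading Q12 as a choice of one whole column does not help: A matches the key at 2 steps, B at 3 and C at 1, so no column is correct.

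**Are the options or the key at fault?** The key names seven different sites once each. The three options at step 4 are already keyed elsewhere (Palms at step 1, Back of hands at 2, Between fingers at 3). The Q9 key runs Finger webs, Back of fingers, Thumbs, Finger tips. That is the Q12 key for steps 3 to 6 in order, if Finger webs and Between fingers mean the same site. The fault is therefore in the options.

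**Q13.** The labels are Finger tips, Back of hands, Thumbs, Palms, Finger tips, Back of fingers, Wrists: six different sites for seven places. Against the Q12 key, one Between fingers is missing and one Finger tips is surplus. The list is identical, in order, to column A of Q12, which suggests that a column of options was copied in as the label list. No cell is missing from either table, so this does not look like a PDF reading fault.

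Over all orderings of these labels, the most that can match the Q12 key is 6 of 7. For a participant who puts the six available sites in the right relative order, the score depends on where the spare Finger tips goes:

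| Place of the spare label | 1 | 2 | 3 | 4 | 5 | 6 | 7 |
|---|---|---|---|---|---|---|---|
| Matches out of 7 | 4 | 5 | 6 | 5 | 4 | 4 | 2 |

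Places 5 and 6 give the same ordering, so there are six distinct orderings.

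**Effect on the between-arm difference in Q12, per-step scoring.** Let the arms differ by *d* at every step. A sound item shows a difference of 7*d* and the printed item shows 6*d*. The loss is 1 − 6/7 = 1/7 = 14.3% in raw points. In standardised terms, with equal variance at each step, the loss is 1 − √(6/7) = 7.4% if the steps are independent and 0% if they are perfectly correlated.

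**All-or-nothing scoring.** Every participant in every arm scores 0 on both items, which then carry no information.

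**The case against.** The mismatches themselves cannot be disputed. The case on the other side is that they matter little.

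- *Step 4 is zero for everyone.* A constant adds nothing to a difference between arms, its standard error or its p-value. This stands: there is no bias between arms, and dropping step 4 gives the same test as leaving it in. The 14% is a loss of raw points against a repaired item; the standardised loss is smaller, at most 7.4% under the assumptions above.
- *The low end of the Q13 range is contrived.* A participant who has learned numbered steps may leave place 3 for the spare label and score 6/7. This partly stands. The document gives no basis for saying how often the lower scores would occur. It remains true that the score among people with the same knowledge turns on how they handle a faulty label.
- *No scoring rule and no Q13 key are printed.* This stands, and the sizes are conditional on it. Without any key, however, Q13 still offers six sites for seven places, and the Q12 mismatch needs no scoring rule.
- *The reach is narrow.* Both items are post-only and nothing makes them a named endpoint. Q6 to Q10 still measure knowledge at both times, and the hand-scanner residual is unaffected. This stands, and it limits the importance of the point.
- *Discarding all of Q13 after use wastes data.* Scoring the relative order of the distinct labels, in the same way in every arm, is equally defensible.

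These points reduce the size of the effect. They do not make the printed instrument correct.

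**Conclusion.** The concern holds and should be fixed. The post-test instrument, as printed, cannot record a fully correct 7-step answer on Q12, nor on Q13 if the Q12 sequence applies to it. Per-step scoring caps each item at 6/7. The cost on Q12 is 14% of the raw between-arm difference if the arms differ equally at every step. All-or-nothing scoring makes both items useless. The error falls equally on all four arms, so its direction is to hide a video effect on these two items.

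The conclusion rests on three assumptions: Q13 is scored against the Q12 key, Finger webs and Between fingers are the same site (this only supports the key), and participants do not see the answer column. The mismatches are certain. Their effect on any overall knowledge score cannot be stated, because no scoring rule is given.

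**What to change.** Before the form is used, put Back of fingers among the options at step 4 of Q12, and replace one of the two Finger tips labels in Q13 with Between fingers. The attainable maximum then rises from 6/7 to 7/7 on each item. Printing the intended key for Q13 would remove the remaining doubt.

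If the form has already been used, exclude step 4 of Q12 and all of Q13 from scoring in every arm, because the missing label can shift the positions of the other steps. A relative-order score for Q13, defined identically for all arms, is an acceptable alternative. Either rule should be fixed without sight of group.

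The cost before use is one edited option and one edited label, with no burden on participants.
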